**Table 10 PCSA Criteria for ECG Test Results**

Test	PCSA Criteria
Heart Rate	≤ 50 bpm and decrease from baseline ≥ 20 bpm ≥ 120 bpm and increase from baseline ≥ 20 bpm
PR Interval	≥ 220 msec and increase from baseline ≥ 20 msec
QRS Interval	≥ 120 msec
QTcF and QTcB absolute	Interval >450 msec and interval ≤ 480 msec Interval >480 msec and interval ≤ 500 msec Interval >500 msec
QTcF and QTcB change from baseline	Increase from baseline > 30 msec and ≤ 60 msec; Increase from baseline > 60 msec

QTc will be corrected based on Fridericia’s formula for QTcF and Bazett's formula for QTcB ( $QTcF = QT / \sqrt[3]{RR}$  and  $QTcB = QT / \sqrt{RR}$ ) where RR=60/HR. Baseline QTcF and QTcB will be derived from the visit that other ECG parameters are flagged as baseline. If there are multiple assessments at the same visit and time point, the average will be calculated for each parameter and used for the analysis.

[figure not shown]
Subjects with notable ECG interval values and qualitative ECG abnormalities will be listed for each subject and time point and the corresponding notable values and abnormality findings will be included in the listings.

[figure not shown]
Unscheduled ECG measurements will not be used in computing the descriptive statistics for change from baseline at each post-baseline time point. However, they will be used in the analysis of notable ECG changes and the shift table analysis of notable QT parameters.

**16.5.2 ECOG Performance Status**

ECOG PS score at Induction Phase baseline and Maintenance Phase baseline will be presented by number and percentage for each treatment arm. In addition, shifts from Maintenance Phase baseline in ECOG PS score will be presented at planned visits during the Maintenance Phase, the Discontinuation visit, and End of Treatment visit by number and percentage for each treatment arm. Please refer to Section 10 for the definition of Maintenance Phase baseline for ECOG PS. Similarly, shifts from baseline to highest ECOG PS score during the Induction Phase and Maintenance Phase will be summarized. ECOG performance status with shift from ECOG=0 or 1 to ECOG 2 or higher will also be presented in a data listing with subject identifier and other relevant information.

[figure not shown]

---

[Redacted]

---

[Redacted]

17

References

1. Wassmer, G. (2006), Planning and Analyzing Adaptive Group Sequential Survival Trials. *Biom. J.*, 48: 714-729.
6. Cochran WG. Some Methods for Strengthening the Common Chi-square Tests. *Biometrics* 1954; 10:417-51.

## 18 Appendices

### Appendix I Clinically Important Protocol Deviations

Description of Protocol Deviation	Deviation Code	Clinically Important PD?
Inclusion / Exclusion criteria		
Subject did not meet inclusion criterion 3, i.e. subject without evaluable PD-L1 expression assessment	INCEXC02	
Subject did not meet inclusion criterion 4, i.e. subject had no measurable disease as per RECIST 1.1	INCEXC03	
Subject did not meet inclusion criterion 5, i.e. subject without histologically confirmed unresectable locally advanced or metastatic adenocarcinoma of the stomach or GEJ	INCEXC04	Yes
Subject did not meet inclusion criterion 8, i.e. subject does not show adequate hematological function as defined in the study protocol.	INCEXC05	
Subject did not meet inclusion criterion 9, i.e. subject does not show adequate hepatic function, as defined in the study protocol.	INCEXC06	
Subject did not meet inclusion criterion 10, i.e. subject does not show adequate renal function, as defined in the study protocol	INCEXC07	
Subject did not meet inclusion criterion 12, i.e. subject refused use of effective contraception, if the risk of conception exists	INCEXC08	
Subject met exclusion criterion 1, i.e. subject received prior therapy with any antibody or drug targeting T-cell coregulatory proteins (immune checkpoints) such as PD-1, PD-L1, or cytotoxic T-lymphocyte antigen-4 (CTLA-4)	INCEXC09	Yes
Subject met exclusion criterion 2, i.e. subject receiving concurrent anticancer treatment (including immune therapy or cytokine therapy except for erythropoietin)	INCEXC10	Yes
Subject met exclusion criterion 3, i.e. subject received prior chemotherapy for unresectable locally advanced or metastatic adenocarcinoma of the stomach or GEJ	INCEXC11	Yes
Subject met exclusion criterion 4, i.e. subject's disease harbors a HER-2 positivity by IHC (≥3+) or FISH (IHC 2+, FISH +)	INCEXC12	
Subject met exclusion criterion 5, i.e. major surgery for any reason, except diagnostic biopsy, within 4 weeks of enrolment and/or if the subject has not fully recovered from the surgery within 4 weeks of enrolment	INCEXC13	
Subject met exclusion criterion 6, i.e. subject received immunosuppressive agents and these drugs were not tapered off before initiation of the trial treatment	INCEXC14	

Description of Protocol Deviation	Deviation Code	Clinically Important PD?
Subject met exclusion criterion 7, i.e. subject has brain metastases not meeting the exceptions laid out in the study protocol	INCEXC15	Yes
Subject met exclusion criterion 8, i.e. subject had previous malignant disease (other than gastric cancer) within the last 5 years, with the exception of basal or squamous cell carcinoma of the skin or carcinoma in situ.	INCEXC16	
Subject met exclusion criterion 10, i.e. subject has significant acute or chronic infections (e.g. HIV, AIDS, HCV, HBV, TB)	INCEXC17	
Subject met exclusion criterion 11, i.e. subject has an active autoimmune disease that might deteriorate when receiving an immunostimulatory agent	INCEXC18	
Subject met exclusion criterion 15, i.e. subject is pregnant or lactating	INCEXC19	
Any other inclusion/exclusion criteria not met and not covered above	INCEXC20/ INCEXC21	
Informed Consent/ Subject information		
Subject did not sign ICF and was enrolled.	INFCON01	
Site Personnel who signed the ICF or performed any study related procedure and is not listed on the Site Delegation Log.	INFCON02	
ICF is signed after study procedure was done, with the exception of assessments such as CT/MRI that were performed as part of normal site procedures. Exempted assessments must have been performed within the 28-day screening window.	INFCON03	
Incorrect version of ICF signed	INFCON04	
Missing Date or Time recorded in the ICF document.	INFCON06	
New ICF version not signed in a timely manner	INFCON07	
Any other informed consent deviation not covered above	INFCON08/ INFCON09	
Subject Visit Schedule		
Subject visits not performed/completed	VISITS01	
No survival information / no collection of additional cancer medication post disease progression. NOTE: if the subject withdrew fully from consent and did not agree to provide follow-up information, there is no PD	VISITS02	
Subject visits performed outside of window (-4/+2 day), except those due to safety reasons e.g. treatment delay due to toxicity	VISITS03	
Investigational Product		
IP preparation, storage and administration of prepared infusion was not according to Protocol/Pharmacy manual	INVPRO01	
Aveluamb infusion rate not performed per protocol (e.g. not between 50-80 min or at a reduced rate if required per safety management)	INVPRO02	

Description of Protocol Deviation	Deviation Code	Clinically Important PD?
IP storage temperature out of range and site used IP or patient received expired IP	INVPRO04	
Subject received wrong treatment per IXRS	INVPRO05	
Subject received an incorrect Avelumab dose	INVPRO06	
Avelumab premedication was administered but not according to the protocol requirements prior to IP dose	INVPRO07	
Chemotherapy premedication was not administered prior to dose or not according to label or local guidelines	INVPRO08	
Avelumab premedication was not administered at all, prior to IP dose	INVPRO09	
IP distributed without IXRS call	INVPRO10	
Subject received an incorrect Physician's choice chemotherapy dose ( $\geq \pm 5$ % assigned dose)	INVPRO11	
Missed chemotherapy dose due to reason other than Adverse Event	INVPRO12	
Missed avelumab dose due to reason other than Adverse Event	INVPRO13	
Concomitant Medications/ Procedures		
Subject took immunotherapy, immunosuppressive drugs (that is, chemotherapy or systemic corticosteroids except for short-term treatment of allergic reactions or for the treatment of irAEs), or other anti-cancer or experimental pharmaceutical products.	CONMED02	
Subject randomized to receive avelumab received treatment with growth factors (granulocyte colony stimulating factor or granulocyte macrophage colony stimulating factor).	CONMED03	
Subject received herbal remedies with immunostimulating properties (for example, mistletoe extract) or known to potentially interfere with major organ function (for example, hypericin) or have abused alcohol or other drugs during the trial	CONMED05	
Subject had major surgery during the study	CONMED06	
Subject received radiation therapy (except for superficial lesions or bone-directed), while on study treatment.	CONMED07	
Other deviation on concomitant medication not covered above	CONMED08/ CONMED09	
Protocol Procedures		
Subject randomized >10 days after re-baseline period started	PROCED02	
Source data not available/ not eligible for CRA review	PROCED03	
Study procedures not done/omitted	PROCED06	
Subject met criteria for permanent withdrawal from trial treatment but treatment was not discontinued	PROCED07	
Contraception not used per protocol requirements	PROCED08	

Description of Protocol Deviation	Deviation Code	Clinically Important PD?
SAEs not reported within the mandated timeframe to Sponsor (e.g. within 24 hours) or SAE follow-up information not provided in a timely manner	PROCED10	
Screening or re-baseline CT/MRI scans not performed	PROCED11	
Screening or re-baseline images (lung/abdomen/pelvis, brain, bone scan if clinically indicated) not performed within required time window. Screening: 28 days (brain 6 weeks). Re-baseline: 10 days	PROCED12	
6-weekly tumor evaluation/staging imaging scan (CT/MRI) not performed at all	PROCED13	
6 weekly Tumor Evaluation/Staging imaging scan (CT/MRI) performed >10 days outside window	PROCED14	
Paper QoL used and the data were moved from the paper QoL to the tablet by the site staff	PROCED16	
Subject randomized despite having disease progression assessed by the independent radiologist	PROCED20	Yes
Laboratory		
Subject enrolled or randomized without all safety lab results available (including pregnancy test for females)	LABPRCO01	
Subject dosed without all safety lab results available (including pregnancy test for females) or not reviewed by the Investigator prior to dosing	LABPRCO02	
Randomization		
Randomization interrupted in IWRS resulting in erroneous application of the randomization code	RANDOM01	Yes
Patient randomized more than once	RANDOM02	
Other		
Any other protocol deviation which is deemed to be significant for a specific subject or for the trial but has not been pre-specified in this table	OTHPRC01/ OTHPRC02	

Appendix II EORTC QLQ-C30 Version 3.0

Table 1: Scoring the QLQ-C30 version 3.0

	Scale	Number of items	Item range*	Version 3.0 Item numbers	Function scales
Global health status / QoL					
Global health status/QoL (revised) †	QL2	2	6	29, 30	
Functional scales					
Physical functioning (revised) †	PF2	5	3	1 to 5	F
Role functioning (revised) †	RF2	2	3	6, 7	F
Emotional functioning	EF	4	3	21 to 24	F
Cognitive functioning	CF	2	3	20, 25	F
Social functioning	SF	2	3	26, 27	F
Symptom scales / items					
Fatigue	FA	3	3	10, 12, 18	
Nausea and vomiting	NV	2	3	14, 15	
Pain	PA	2	3	9, 19	
Dyspnoea	DY	1	3	8	
Insomnia	SL	1	3	11	
Appetite loss	AP	1	3	13	
Constipation	CO	1	3	16	
Diarrhoea	DI	1	3	17	
Financial difficulties	FI	1	3	28	

\* *Item range* is the difference between the possible maximum and the minimum response to individual items; most items take values from 1 to 4, giving *range* = 3.

† (revised) scales are those that have been changed since version 1.0, and their short names are indicated in this manual by a suffix "2" – for example, PF2.

For all scales, the *RawScore*, *RS*, is the mean of the component items:

$$RawScore = RS = (I_1 + I_2 + \dots + I_n) / n$$

Then for **Functional scales**:

$$Score = \left\{ 1 - \frac{(RS - 1)}{range} \right\} \times 100$$

and for **Symptom scales / items** and **Global health status / QoL**:

$$Score = \{(RS - 1) / range\} \times 100$$

**Examples:**

Emotional functioning

$$RawScore = (Q_{21} + Q_{22} + Q_{23} + Q_{24}) / 4$$

$$EF\ Score = \{1 - (RawScore - 1) / 3\} \times 100$$

Fatigue

$$RawScore = (Q_{10} + Q_{12} + Q_{18}) / 3$$

$$FA\ Score = \{(RawScore - 1) / 3\} \times 100$$

Table 1: Scoring the QLQ-C30 version 3.0

	Scale	Number of items	Item range*	Version 3.0 Item numbers	Function scales
Global health status / QoL					
Global health status/QoL (revised) †	QL2	2	6	29, 30	
Functional scales					
Physical functioning (revised) †	PF2	5	3	1 to 5	F
Role functioning (revised) †	RF2	2	3	6, 7	F
Emotional functioning	EF	4	3	21 to 24	F
Cognitive functioning	CF	2	3	20, 25	F
Social functioning	SF	2	3	26, 27	F
Symptom scales / items					
Fatigue	FA	3	3	10, 12, 18	
Nausea and vomiting	NV	2	3	14, 15	
Pain	PA	2	3	9, 19	
Dyspnoea	DY	1	3	8	
Insomnia	SL	1	3	11	
Appetite loss	AP	1	3	13	
Constipation	CO	1	3	16	
Diarrhoea	DI	1	3	17	
Financial difficulties	FI	1	3	28	

\* *Item range* is the difference between the possible maximum and the minimum response to individual items; most items take values from 1 to 4, giving *range* = 3.

† (revised) scales are those that have been changed since version 1.0, and their short names are indicated in this manual by a suffix "2" – for example, PF2.

For all scales, the *RawScore*, *RS*, is the mean of the component items:

$$RawScore = RS = (I_1 + I_2 + \dots + I_n) / n$$

Then for **Functional scales**:

$$Score = \left\{ 1 - \frac{(RS - 1)}{range} \right\} \times 100$$

and for **Symptom scales / items and Global health status / QoL**:

$$Score = \{(RS - 1) / range\} \times 100$$

**Examples:**

Emotional functioning

$$RawScore = (Q_{21} + Q_{22} + Q_{23} + Q_{24}) / 4$$

$$EF\ Score = \{1 - (RawScore - 1) / 3\} \times 100$$

Fatigue

$$RawScore = (Q_{10} + Q_{12} + Q_{18}) / 3$$

$$FA\ Score = \{(RawScore - 1) / 3\} \times 100$$

## Appendix III EORTC QLQ-C30-STO22: Gastric Cancer Module

### Gastric cancer module: QLQ-STO22

#### Scope

The gastric cancer module is meant for use among patients with gastric cancer varying in disease stage and treatment modality (i.e. surgery, chemotherapy, radiotherapy, etc.). It should always be complemented by the QLQ-C30.

#### Scoring

	Scale name	Number of items	Item range	QLQ-STO22 item numbers
Functional scales				
Body image	STOBI	1	3	49
Symptom scales				
Dysphagia	STODYS	3	3	31 – 33
Pain	STOPAIN	4	3	34 – 37
Reflux symptoms	STORFX	3	3	38 – 40
Eating restrictions	STOeat	4	3	41 to 43,46
Anxiety	STOANX	3	3	47,48,50
Dry mouth	STODM	1	3	44
Taste	STOTA	1	3	45
Body image	STOBI	1	3	49
Hair loss	STOHL	2/1	3	51,52*

#### Remarks

- Item 52 is an optional item and depends on the answer to item 51. Item 52 should only be answered and assessed if 'yes' has been answered to item 51.

## Appendix IV Description of the Case Definition for Assessment of Immune-Related AEs and IRRs

### Immune-Related Adverse Events

Immune-related adverse events (irAEs) will be identified programmatically. AEs which satisfy all of the following criteria will be flagged as immune-related:

- 1) The AE preferred term matches a preferred term on the list of pre-selected MedDRA terms.
- 2) The AE onset occurs after the first study drug administration and no more than 90 days after last dose.
- 3) On the AE eCRF page, the question “Were Corticosteroids, Immunosuppressants, or hormonal therapy (e.g. Thyroid) applied?” has the answer “Yes” selected.
- 4) On the AE eCRF page, either:
  - a. The question “Does any of the following provide a clear etiology for the event?” has the answer “No” selected, indicating that the AE is not attributable to underlying cancer disease/PD, prior or concomitant medications/procedures, nor another medical condition such as an infection or pre-existing disease.

OR

- b. The AE eCRF indicates that a biopsy was performed and the question “Is the histopathology/biopsy consistent with an immune-mediated event?” has the answer “Yes” selected.

In the case that criteria (1) through (3) are met, and entries for condition (4) are missing, the following rules will be applied:

- If the answer to “Does any of the following provide a clear etiology for the event?” (4a) is missing, the event will be considered as irAE (irrespective of biopsy results).
- If the answer to “Is the histopathology/biopsy consistent with an immune-mediated event?” (4b) is missing, or if no biopsy was performed, and condition (4a) is not satisfied (i.e. “Yes” is selected as the answer to the question “Does any of the following provide a clear etiology for the event?”), the event will be considered as a non-irAE.

### IRRs

Infusion related reactions are identified based on a list of MedDRA PTs and criteria on the timely relationship according to Table 15.

**Table 15 Criteria for infusion related reactions**

---

Infusion related reactions	
Reactions - Considered when onset is on the day of study drug infusion (during or after the infusion) or the day after the study drug infusion (irrespective of resolution date):
 

• Infusion related reaction

• Drug hypersensitivity

• Anaphylactic reaction

• Hypersensitivity

• Type 1 hypersensitivity

 
Signs and Symptoms - occurring on the day of study drug infusion (during or after the infusion) and resolved with end date within 2 days after onset
 

• Pyrexia

• Chills

• Flushing

• Hypotension

• Dyspnoea

• Wheezing

• Back pain

• Abdominal pain

• Urticaria

----------------------------	--

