#### **Adverse events**

Incomplete AE-related dates will be imputed as follows:

- If the AE onset date is missing completely, then the onset date will be replaced by the start of randomized treatment.
  - If only the day part of the AE onset date is missing, but the month and year are equal to the start of randomized treatment, then the AE onset date will be replaced by the start of randomized treatment. For example, if the AE onset date is --/JAN/2015, and randomized treatment start date is 15/JAN/2015, then the imputed AE onset date will be 15/JAN/2015.
  - If both the day and month of the AE onset date are missing but the onset year is equal to the start of randomized treatment, then the onset date will be replaced by the start of randomized treatment.
-

For example, if AE onset date is --/---/2014, and randomized treatment start date is 19/NOV/2014, then the imputed AE onset date will be 19/NOV/2014.

- In all other cases, the missing onset day or missing onset month will be replaced by 1.
- Incomplete stop date will be replaced by the last day of the month (if day is missing only), if not resulting in a date later than the date of subject's death. In the latter case, the date of death will be used to impute the incomplete stop date.
- In all other cases, the incomplete stop date will not be imputed.

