## 16.1 Adverse Events

Treatment-emergent adverse events (TEAEs) are those events with onset dates occurring during the on-treatment period or if the worsening of an event is during the on-treatment period. In this study, there are two on-treatment periods, one for Induction Phase and one for Maintenance Phase.

All analyses described will be based on TEAEs (started during the on-treatment period) if not otherwise specified. The AE listings will include all AEs (whether treatment-emergent or not). AEs outside the on-treatment period will be flagged in the listings.

- **Related Adverse Events:** adverse events with relationship to study treatment (as recorded on the AE eCRF page, Relationship with study treatment = Related) reported by the investigator and those of unknown relationship (i.e. no answer to the question “Relationship with study treatment”).
- **Serious Adverse Events (SAE):** serious adverse events (as recorded on the AE eCRF page, Serious Adverse Event = Yes).
- **Adverse Events Leading to Treatment Discontinuation:** adverse events leading to permanent discontinuation of study treatment (as recorded on the AE eCRF page, Action taken with study treatment = Drug withdrawn).
- **Adverse Events Leading to Death:** adverse event leading to death (as recorded on the AE eCRF page, Outcome = Fatal, as well as AEs of Grade 5).
- **Immune Related Adverse Events (irAEs):** immune related adverse events are identified via customized MedDRA PT queries and additionally classified by medical assessment according to case definition (two level approach). Details are included in [Appendix IV](#).
- **Infusion Related Reactions (IRRs):** IRRs are identified based on a list of MedDRA PTs. The detailed criteria of the timing relationship to infusion are specified in [Table 14](#) of Appendix IV.

Unless otherwise specified, AEs will be summarized by number and percentage of subjects with the AE in the category of interest as described above, by treatment group, primary System Organ Class (SOC) and Preferred Term (PT) and by decreasing frequency based on the avelumab treatment arm.

Each subject will be counted only once within each SOC or PT. If a subject experiences more than one AE within a SOC or PT for the same summary period, only the AE with the strongest relationship or the worst severity, as appropriate, will be included in the summaries of relationship and severity.

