### **16.2.3 Other Significant Adverse Events**

*Analysis sets: Safety-Maintenance Analysis Set*

The following tables will be created for Maintenance Phase treatment-emergent irAEs by treatment group. Separate summary tables will present potential irAEs (those identified solely by MedDRA preferred term) and medically assessed irAEs (which meet the criteria outlined in [Appendix IV](#)). For the potential irAE tables, both treatment arms will be presented with counts, as applicable. Only the counts for the avelumab arm will be displayed in the medically assessed irAE summary tables. “Cluster” is a compilation of PTs that are categorized by immune-related event of special interest.

- The overall summary of irAEs table will include the following categories:
  - All irAEs
  - irAEs leading to death, by Cluster and PT
  - irAEs, by Cluster and PT

- irAEs, Grade  $\geq 3$ , by Cluster and PT
- irAEs leading to permanent treatment discontinuation, by Cluster and PT
- irAEs by Cluster and PT and worst grade
- irAEs leading to death, by Cluster and PT
- irAEs by Cluster and PT
- irAEs, grade  $\geq 3$ , by Cluster and PT
- irAEs leading to permanent treatment discontinuation by Cluster and PT
- irAEs by Cluster and PT and worst grade

A listing of all potential and reviewed irAEs will be provided with the relevant information and a flag for irAEs with onset outside of the on-treatment period.

The frequency (number and percentage) of subjects with each of the following will be presented for treatment emergent IRRs, by treatment group:

- The overall summary of IRR table will include the following categories:
    - All IRRs
    - Related IRRs
    - Serious IRRs
    - Related serious IRRs
    - IRRs, Grade  $\geq 3$
    - Related IRRs, Grade  $\geq 3$
    - IRRs leading to permanent treatment discontinuation
    - Related IRRs leading to permanent treatment discontinuation
    - IRRs leading to death
    - Related IRRs leading to death
  - IRRs leading to death, by PT
  - Related IRRs leading to death, by PT
  - IRRs, by PT
  - IRRs, Grade  $\geq 3$ , by PT
  - Related IRRs, by PT
  - Related IRRs, Grade  $\geq 3$ , by PT
  - IRRs leading to permanent treatment discontinuation, by PT
-

- Related IRRs leading to permanent treatment discontinuation, by PT
- Serious IRRs, by PT
- Related serious IRRs, by PT
- Time related to first onset of an IRR (infusion 1, infusion 2, infusion 3, infusion 4 or later)

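### The 2-day resolution limit on nine infusion-day symptoms keeps persistent, ongoing and (as worded) fatal symptom-coded events out of the planned infusion-related reaction tables

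*SAP*

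**What the plan says.** SAP Appendix IV defines IRRs by rule: "Infusion related reactions are identified based on a list of MedDRA PTs and criteria on the timely relationship". SAP 16.1 says the same, though it cites the criteria as Table 14 where the appendix numbers them Table 15.

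Table 15 has two tiers:

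- **Five reaction terms** (infusion related reaction, drug hypersensitivity, anaphylactic reaction, hypersensitivity, type 1 hypersensitivity). Onset may be on the infusion day or "the day after the study drug infusion (irrespective of resolution date").
- **Nine signs and symptoms** (pyrexia, chills, flushing, hypotension, dyspnoea, wheezing, back pain, abdominal pain, urticaria). Onset must be on the infusion day, during or after the infusion, "and resolved with end date within 2 days after onset".

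SAP 16.2.3 builds all IRR output from the events so identified: any grade, Grade 3 or higher, serious, discontinuation and fatal, most of them also for related events. Examples are "IRRs leading to permanent treatment discontinuation, by PT" and "Related serious IRRs, by PT". A listing of IRRs follows.

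For immune-related events, the same section plans two versions: "Separate summary tables will present potential irAEs (those identified solely by MedDRA preferred term) and medically assessed irAEs".

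**The concern.** A time limit on non-specific symptoms is a reasonable filter in gastric cancer, where abdominal pain or dyspnoea on an infusion day may be due to the disease. The difficulty is that the filter uses the course of the event, and the tables built on it report severity and outcome. For the nine symptom terms, whether an event is a case depends partly on the result being tabulated. The rule has no override for grade, seriousness, action taken or outcome, and the visible text plans no medical review of IRRs.

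What is at stake is the description of a named risk. Protocol 3.5 lists infusion-related reactions as one of two primary known identified risks of avelumab, and Protocol 7.4.1.1 makes them an adverse event of special interest. Protocol 6.5.4.1 ends avelumab after a Grade 3 or 4 reaction, and after a second reaction of Grade 2 or higher at the slower rate. The severe and discontinuation rows therefore describe the reactions that end treatment.

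**Working it through.** The plan states no figure to reproduce. The check applies Table 15 to an event with onset during an infusion, for example dyspnoea, under two ways of coding it.

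| Course of the event | Coded to one of the nine symptoms | Coded to one of the five reaction terms |
|---|---|---|
| Resolved, end date no later than onset + 2 days | Counted | Counted |
| Resolved, end date later than onset + 2 days | Not counted | Counted |
| Ongoing, no end date | Not counted | Counted |
| Fatal | Not counted as worded | Counted |

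**Ongoing events.** SAP 10 imputes an adverse event stop date only when the day alone is missing. An ongoing event has no end date and fails the condition.

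**Fatal events.** SAP 16.1 identifies an event leading to death by "Outcome = Fatal, as well as AEs of Grade 5". Table 15 requires a symptom to have resolved. As worded the two conditions do not overlap, so the nine terms contribute 0 to the fatal IRR rows. A program that tested only the end date could keep a death within 2 days of onset. SAP 10 can supply such a date: when the day is missing and month-end would fall after death, "the date of death will be used to impute the incomplete stop date".

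**Where the excluded events still appear:**

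- The general tables of treatment-emergent, serious, discontinuation and fatal events (SAP 16.1.1, 16.1.2, 16.2.2). These are arranged by system organ class and preferred term and do not link events to infusions.
- The listings of all adverse events (SAP 16.1), discontinuation events (16.1.2), serious events (16.2.2) and study drug administration (SAP 14).
- The death listing in SAP 16.2.1, which shows fatal event terms with first and last dose dates and flags deaths within 30 days of the last dose.

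An excluded event can therefore be found by matching listings by hand. No visible planned table counts such events by infusion day.

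**Scale.** Protocol 8.1 gives 499 subjects randomized 1:1, so 499 / 2 = 249.5 per arm. Assuming nearly all avelumab subjects are dosed:

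- 1 / 249.5 = 0.40 percentage points for each subject whose only qualifying event is excluded.
- 5 / 249.5 = 2.00 percentage points for five such subjects.

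The range of 1 to 5 subjects is an assumption for illustration. The documents give no count.

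**The case against.** **The limit is a choice for specificity.** This stands. It is why Table 15 should remain the main definition. Two versions for immune-related events do not oblige the sponsor to give two for IRRs; they only show that the format is already in use in the same section.

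**A recognised reaction would be reported as a reaction.** The discontinuation rule in Protocol 6.5.4.1 operates when the investigator judges the event to be infusion-related. Such an event would naturally be coded to one of the five reaction terms, which have no resolution limit. Protocol 7.4.1.1 likewise asks for the primary cause of death as the fatal event. This is plausible and is the main reason the number lost may be small. The documents do not guarantee it, and the eCRF completion conventions are not available.

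**Nothing is lost from the report.** A reader might infer that severe or fatal infusion reactions would disappear. The documents do not support that: the general tables and the listings named above retain them, and the death listing sets fatal terms beside dosing dates. What is missing is a summary.

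**Removing the limit has its own flaw.** SAP 10 moves a wholly missing adverse event onset date to the start of randomized treatment, and does the same when the known month and year, or the year alone, match that start. A persistent symptom can thus be placed on the first infusion day when it began on another day. A table without the resolution limit would count it, including in the Grade 3 or higher and serious rows. This objection is right, and the fix excludes imputed onset dates.

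**Redaction.** The SAP contents page shows a redacted entry between 16.2.3 and 16.3, so statements about what is planned hold for the visible text only.

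**Conclusion.** The point holds as a limited gap in safety reporting. For nine symptom terms, the Grade 3 or higher, serious, discontinuation and fatal IRR tables, and the IRR listing, omit infusion-day events that last more than 2 days, are ongoing or, as worded, are fatal. Compared with the same definition without the limit, these counts can only be equal or lower. The size is unknown: about 0.4 points per affected subject, and possibly no subjects at all. Safety is tabulated descriptively (SAP 16), so no test or primary conclusion changes.

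Three stronger readings are not supported:

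- That the tables understate true infusion reactions. The direction is unknown, because short unrelated symptoms on an infusion day are counted.
- That the limit systematically removes Grade 3 reactions because Protocol 6.5.4.1 describes them as prolonged. Prolonged there need not mean more than 2 days.
- That the merging of consecutive records in SAP 16.1 lengthens events past the limit. The SAP does not say that Table 15 tests the merged end date, so nothing here rests on it.

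**What to change.** Keep Table 15 as the main definition and leave the planned IRR tables unchanged. Add one supplementary table to SAP 16.2.3, worded for example as follows:

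*The nine Table 15 signs and symptoms with a recorded (not imputed) onset date on an infusion day, during or after the infusion, will be summarized regardless of when or whether they resolved and regardless of outcome. The table will be given by treatment group, for all and for related events, with rows for any grade, Grade 3 or higher, serious, permanent discontinuation, and death. The number of events left out because the onset date was imputed under Section 10 will be reported.*

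Label it as a more sensitive and less specific definition, as potential irAEs are shown beside medically assessed ones.

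The cost is one extra table programmed before database lock from data already recorded: onset, infusion dates, grade, seriousness, action taken, outcome and relationship. The downside is that it will include some disease-related symptoms, which is why the label is needed. Comparability with other analyses that use Table 15 is unaffected.
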